#### 7.1.4 Instructions for Dispensation, Use, and Administration

- At Visit 1, qualified subjects will be assigned a vehicle kit. Subjects will use two vials from the kit for Visit 1 in-office doses. After use, vials will be placed into a zip locked bag labeled with subject's initials and screening number for accountability.
- At Visit 2, qualified subjects will be randomized and will be assigned a single kit of 2 pouch supply of Reproxalap Ophthalmic Solution 0.25% or Vehicle. Subjects will be dosed in office four times (QID) by trained site staff.
- At Visit 3, subjects will be dosed three times in-office from the same kit by trained site staff.
- Subjects will be instructed to close their eyes for two minutes after instillation.

#### 7.2 Other Study Supplies

Tear collection supplies, Schirmer's Test strips, Scale to weigh Schirmer's strips, 2% preservative-free sodium Fluorescein Solution, Fluorescein Strips, ETDRS Series 2000 Chart 1 & Chart 2, eye occluder, alcohol swabs.

# 8 STUDY METHODS AND PROCEDURES

#### 8.1 Subject Entry Procedures

8.1.1 Overview

Subjects as defined by the criteria in section 5.2, 5.3, and 5.4 will be considered for entry into the trial.

#### 8.1.2 Informed Consent

Prior to each subject's participation in the clinical trial (i.e., changes in a subject's medical treatment and/or study related procedures), the clinical trial will be discussed with the subjects, and subjects wishing to participate must give written informed consent using an informed consent form. The informed consent form must be the most recent version that has received approval/favorable review by a properly constituted Independent Review Board.

#### 8.1.3 Washout Intervals

Prohibited medications, treatments, and activities are outlined in the exclusion criteria.

#### 8.1.4 Procedures for Final Study Entry

Subjects must satisfy all of the inclusion criteria and none of the exclusion criteria in order to be entered into the study.

#### 8.1.5 Methods for Assignment to Treatment Groups:

At Visit 1 each subject who signs the informed consent will be assigned a screening number. All screening numbers will be assigned in strict numerical sequence at each site and no numbers will be skipped or omitted.

At Visit 2, a patient who meets all the eligibility criteria will be randomized to receive treatment reproxalap or vehicle in a 1:1 ratio. Patients will be assigned a randomization number and kit number via IWRS.

The site staff will dispense to the patient the study kit labeled with the corresponding kit number. Both the randomization number and the dispensed study drug kit number will be recorded on the patient's source document and eCRF.

#### 8.2 Concurrent Therapies

The use of any applicable concurrent medications, prescription or OTC medications is to be recorded on the subject's source document along with the reason the medication was taken.

Concurrent enrollment in an investigational drug or medical device study is not permitted.

#### 8.2.1 Prohibited Medications/Treatments

Prohibited medications, treatments, and activities are outlined in the exclusion criteria.

8.2.2 Escape Medications

Not applicable.

8.2.3 Special Diet or Activities

Not applicable.

#### 8.3 Examination Procedures

8.3.1 Procedures to be Performed at the Study Visit with Regard to Study Objective(s)

Visit 1 (Day -14 -16/+2, Screening)

- Informed Consent and HIPAA
- Demographics
- Medical/Medication & Ocular History
- Urine Pregnancy Test (as needed)
- Symptom Questionnaires:
  - Ocular Discomfort & 4-Symptom Questionnaire
  - Ora Calibra® Ocular Discomfort Scale
  - Ocular Dryness Visual Analog Scale
  - Ora Calibra® Conjunctival Allergen Challenge Ocular Itching Scale
- Visual Acuity (ETDRS)

- Slit Lamp Biomicroscopy with Conjunctival Redness assessment
- Fluorescein Staining using the Ora Calibra® Corneal and Conjunctival Staining Scale
- Inclusion/Exclusion Criteria Review
- In-Office Vehicle Instillation by trained site staff

CAE Ex	posure		
	_		

• Slit Lamp Biomicroscopy with Conjunctival Redness assessment

- Schirmer's Test
- Intraocular Pressure
- Dilated Exam
- Schedule for Visit 2

#### Visit 2 (Day 1, Baseline and In-Office Dosing)

- Medical/Medication Update
- Adverse Event Query
- Visual Acuity (ETDRS)
- Slit Lamp Biomicroscopy
- Symptom Questionnaires
  - o Ocular Discomfort & 4-Symptom Questionnaire
  - Ora Calibra® Ocular Discomfort Scale
  - Ocular Dryness Visual Analog Scale
  - Ora Calibra® Conjunctival Allergen Challenge Ocular Itching Scale
- Conjunctival Redness Photography
- Inclusion/Exclusion Criteria Review
- Randomization/Enrollment
- Pre-dose #1 Schirmer's Test
- In-Office Dose #1

- Post-dose #1 Schirmer's Test
- Pre-dose #2 Tear Collection
- In-Office Dose # 2
- Post-dose #2 Tear Collection

- Pre-dose #3 Tear Collection
- In-Office Dose #3
- Post-dose #3 Tear Collection
- In-Office Dose #4
- Conjunctival Redness Photography

- Symptom Questionnaires
  - Ocular Discomfort & 4-Symptom Questionnaire
  - Ocular Discomfort
  - Ocular Dryness Visual Analog Scale
  - Ora Calibra® Conjunctival Allergen Challenge Ocular Itching Scale

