# 4 OVERALL STUDY DESIGN

ADX-102-DED-024 is a Phase 2, multi-center, randomized, double-masked, parallel design, vehicle-controlled trial designed to evaluate the efficacy and safety of 0.25% Reproxalap Ophthalmic Solution compared to vehicle in subjects with dry eye disease. Approximately 150 subjects will be enrolled in the study. Male and female subjects at least 18 years of age with a subject-reported history of dry eye disease in both eyes and meeting all other eligibility criteria will be randomized to receive reproxalap or vehicle in a 1:1 ratio (approximately 75 subjects in each treatment group).

Visit 1 (Day -14 -16/+ 2): Screening	
 
Informed Consent
 
Demographics, Medical/Medication & Ocular History
 
Urine Pregnancy Testing (as needed)
 
Symptom Questionnaires, Ocular Dryness VAS, Visual Acuity
 
Ora Calibra® Conjunctival Allergen Challenge Ocular Itching Scale
 
Slit Lamp Exam with Conjunctival Redness assessment
 
In-Office vehicle dose
 
CAE exposure with Ocular Dryness VAS, Ora Calibra® Ocular Discomfort Scale, and Conjunctival Redness Assessment
 
Slit Lamp Exam
 
Ora Calibra® Corneal and Conjunctival Staining Scale
 
Schirmer's Test
 
IOP and Dilated Fundoscopy
 
			
Visit 2 (Day 1): Randomization/Baseline	
 
Medical/Medication Update: AE Query
 
Visual Acuity
 
Slit Lamp Exam
 
Symptom Questionnaires at specified time points
 
Conjunctival Redness
 
In-Office Doses (QID)
 
Tear Collection & Schirmer's Test
 
			
Visit 3 (Day 2): CAE	
 
Medical/Medication Update: AE Query
 
Urine Pregnancy Testing (as needed)
 
Visual Acuity, Slit Lamp Exam
 
Symptom Questionnaires
 
Conjunctival Redness at specified time points
 
In-Office Doses (
 
			

 
Tear Collection
 
IOP and Dilated Fundoscopy
 
Study Exit
 

---

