### 6.4 Exploratory Endpoints

- Change in tear RASP levels
- Conjunctival redness, Ora Calibra® Ocular Discomfort Scale, and visual analog scale dryness score

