### Visit 3 (Day 2, CAE®)

- Medical/Medication Update
- Adverse Event Query
- Urine Pregnancy Test (as needed)
- Visual Acuity (ETDRS)
- Slit Lamp Biomicroscopy
- Conjunctival Redness Photography
- Symptom Questionnaires:
  - Ocular Discomfort & 4-Symptom Questionnaire
  - Ora Calibra® Ocular Discomfort Scale
  - Ocular Dryness Visual Analog Scale
  - Ora Calibra® Conjunctival Allergen Challenge Ocular Itching Scale
- Pre-dose #1 Tear Collection
- In-Office Dose #1
  - CAE Exposure with:
    - Ocular Dryness Visual Analog Scale
    - Ora Calibra® Ocular Discomfort Scale
    - Conjunctival Redness
- In-Office Dose #2
- Post-CAE exit Tear Collection
- In-Office Dose #3
- Symptom Questionnaires started
  - Ocular Discomfort & 4-Symptom Questionnaire
  - Ocular Discomfort
  - Ocular Dryness Visual Analog Scale
  - Ora Calibra® Conjunctival Allergen Challenge Ocular Itching Scale
- Post-Dose #3 Tear Collection
- Slit Lamp Biomicroscopy

- Intraocular Pressure
- Dilated Exam
- Study Exit

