9.3 Definition of Baseline

Baseline is defined as the last measurement prior to the first dose of study treatment,

Change from baseline will be calculated as post-baseline measurement – baseline measurement.

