14.2.5 CONJUNCTIVAL ALLERGEN CHALLENGE OCULAR ITCHING SCALE (ORA CALIBRA® SCALE)
14.2.5.1 Conjunctival Allergen Challenge Ocular Itching Scale (Ora Calibra [®] Scale)

		A subject lis	sting of the Co	njunctival A	llergen
Challenge Ocular Itching Scale w	ill be generated.				
14.2.5.2 Conjunctival A	LLERGEN CHALLENGE	Ocular Itching	Scale (Ora	CALIBRA®	SCALE)
 14.3 Exploratory Analyses 14.3.1 TEAR REACTIVE ALDEHYDI Tears will be collected from bo 	E SPECIES				
concreted		A subject	listing of the	tear RASP	will be
	/®	\ 			
For conjunctival redness					

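### Does the exploratory tear RASP endpoint fail because no listed tear sample is taken before the first randomised dose?

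*Protocol*

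**What the plan says.** Protocol section 6.4 lists the exploratory endpoint as "Change in tear RASP levels". Section 8.3.1 gives the order of procedures. At Visit 2, Schirmer's Test is done before and after dose #1, and the first tear sample is "Pre-dose #2 Tear Collection". Samples follow after dose #2, then "Pre-dose #3 Tear Collection", then after dose #3. At Visit 3 the samples are "Pre-dose #1 Tear Collection", "Post-CAE exit Tear Collection" and one after dose #3. Neither the Visit 1 list in section 8.3.1 nor the Visit 1 row in section 4 shows a tear collection.

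SAP section 9.3 begins: "Baseline is defined as the last measurement prior to the first dose of study treatment". The visible sentence stops at a comma. It then defines change from baseline as the later value minus baseline. SAP section 14.3.1 on RASP opens with "Tears will be collected from", and almost everything after that is redacted. SAP section 20 plans a RASP table (14.2.5.1, ITT, observed data) whose title breaks off, and section 21 plans a listing (16.2.6.10).

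**The concern.** A change score needs a reference value, and the SAP's general rule places that value before any study treatment. On the visible schedule no tear sample qualifies. The earliest sample already follows one randomised dose, so it is a post-treatment variable that may differ between arms because of the drug. SAP section 11.3 also promises summaries of baseline efficacy variables, and RASP would have nothing to put there.

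If some of the dose #1 effect lasts until the sample before dose #2, subtracting that sample removes part of the effect being sought. Using it as a covariate removes a smaller part. SAP section 2 names tear RASP among the measures of efficacy, so a diluted estimate could be read as weak activity on the drug's target. The change that suggests itself is to make a between-arm comparison of RASP levels the main RASP analysis and to rule out the first sample as baseline or covariate.

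**Working it through.** **Order of samples.** Randomised doses given before each tear collection, counted from the lists in Protocol section 8.3.1:

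| Tear sample | Doses before it |
|---|---|
| Visit 2, before dose #2 | 1 |
| Visit 2, after dose #2 | 2 |
| Visit 2, before dose #3 | 2 |
| Visit 2, after dose #3 | 3 |
| Visit 3, before dose #1 | 4 |
| Visit 3, after CAE exit | 6 |
| Visit 3, after dose #3 | 7 |

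None of the seven has zero. The last two counts use the three Visit 3 doses in sections 7.1.4 and 8.3.1. The synopsis gives one dose on Day 2, a separate inconsistency that cannot alter the finding of no sample before dose #1.

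**What a reference taken after dose #1 would cost.** The documents give no RASP effect, variance or correlation, so there is no plan figure to reproduce. The only input from the documents is "approximately 75 subjects in each treatment group" (Protocol section 4). The rest is assumed for illustration: one RASP value per subject and time, equal SDs (set to 1), a between-arm effect of 0.5 SD, two-sided 0.05, a fraction r of the effect still present before dose #2, and within-subject correlation rho.

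- Levels: effect 0.5, variance 1. Noncentrality is 0.5 / sqrt(2/75) = 0.5 / 0.163 = 3.06, with 148 df. Power is 86%.
- Raw change from the first sample: effect 0.5(1 - r), variance 2(1 - rho).
- First sample as covariate: effect 0.5(1 - rho × r), variance 1 - rho².

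| | r = 0 | r = 0.10 | r = 0.25 | r = 0.50 |
|---|---|---|---|---|
| Effect kept, raw change | 100% | 90% | 75% | 50% |
| Effect kept, covariate, rho 0.5 | 100% | 95% | 87.5% | 75% |
| Power, levels | 86% | 86% | 86% | 86% |
| Power, raw change, rho 0.5 | 86% | 78% | 63% | 33% |
| Power, covariate, rho 0.3 | 89% | 87% | 84% | 77% |
| Power, covariate, rho 0.5 | 94% | 92% | 87% | 75% |
| Power, covariate, rho 0.7 | 99% | 98% | 94% | 79% |

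The r at which each analysis has the same power as levels follows from equating the ratios of effect to SD:

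- Raw change: r = 1 - sqrt(2(1 - rho)). This is 0 at rho = 0.5 and 0.225 at rho = 0.7.
- Covariate: r = (1 - sqrt(1 - rho²)) / rho. This is 0.15, 0.27 and 0.41 at rho = 0.3, 0.5 and 0.7.

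Below those values of r the analysis using the first sample has more power than levels; above them it has less. Dropping the covariate multiplies the SE by 1 / sqrt(1 - rho²), which is 1.05, 1.15 and 1.40 at the same three correlations.

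**What the visible wording implies about the reference.** The synopsis attaches change from baseline to Schirmer's Test, which does have a pre-dose #1 value. The visible RASP wording has no such phrase. Tears are sampled on both sides of Visit 2 doses #2 and #3, and before dosing and after CAE exit at Visit 3. For a change across one dose, or across the challenge, the sample before that dose is the right reference and the SAP 9.3 baseline is not needed.

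**The case for a change.** The strongest case for acting has four parts. The sample order is plain on the page. The general baseline rule cannot be met for RASP. A comparison of levels between randomised arms is unbiased whatever the carry-over. The remedy would be SAP wording only, with no new samples. The three pre-dose samples already planned would also allow carry-over to be estimated, with a 95% CI half-width of 1.976 × 0.163 = 0.32 SD at one sample.

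The sequence stands, and so does the attenuation if the first sample were used as an untreated baseline. What does not stand is the step to a fault in the SAP. No visible text says that this sample is the baseline. The rest of the 9.3 sentence, most of 14.3.1, Protocol Appendix 1 and SAP Table 2 are not visible, and text removed from the public copy cannot be counted as missing from the plan. If the intended quantity is a within-dose change, a result of 1 - r is not bias; it answers a different question from the total effect.

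A ban on the first sample as covariate is not justified either. At modest carry-over the covariate analysis has as much power as levels or more, in exchange for an estimate attenuated by rho × r. A comparison of levels may in any case already be reported: SAP section 9.4 presents summaries by treatment group and, where suitable, by visit, and a RASP table and listing are planned.

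**Conclusion.** No change to the plan follows. The visible schedule has no tear sample before the first randomised dose (0 of 7), so a RASP result should be read as change on treatment, not as change from an untreated baseline. That is a matter of labelling, which analysts can settle when they name the reference sample for the RASP table, and the redacted text may already do so. Whether levels, raw change or covariate adjustment is best depends on r and rho, which the documents do not give. Over the assumed range (r from 0 to 0.50), power at rho = 0.5 runs from 94% to 75% with the covariate and from 86% to 33% for raw change, against 86% for levels. Only raw change loses heavily, and nothing visible shows that it is planned from the first sample. These figures assume 75 per arm, a 0.5 SD effect and equal SDs, and they illustrate the trade-off without deciding the question. The endpoint is exploratory, so the primary, secondary and safety conclusions do not depend on the choice.

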### Visit 3 (Day 2, CAE®)

- Medical/Medication Update
- Adverse Event Query
- Urine Pregnancy Test (as needed)
- Visual Acuity (ETDRS)
- Slit Lamp Biomicroscopy
- Conjunctival Redness Photography
- Symptom Questionnaires:
  - Ocular Discomfort & 4-Symptom Questionnaire
  - Ora Calibra® Ocular Discomfort Scale
  - Ocular Dryness Visual Analog Scale
  - Ora Calibra® Conjunctival Allergen Challenge Ocular Itching Scale
- Pre-dose #1 Tear Collection
- In-Office Dose #1
  - CAE Exposure with:
    - Ocular Dryness Visual Analog Scale
    - Ora Calibra® Ocular Discomfort Scale
    - Conjunctival Redness
- In-Office Dose #2
- Post-CAE exit Tear Collection
- In-Office Dose #3
- Symptom Questionnaires started
  - Ocular Discomfort & 4-Symptom Questionnaire
  - Ocular Discomfort
  - Ocular Dryness Visual Analog Scale
  - Ora Calibra® Conjunctival Allergen Challenge Ocular Itching Scale
- Post-Dose #3 Tear Collection
- Slit Lamp Biomicroscopy

- Intraocular Pressure
- Dilated Exam
- Study Exit

#### **Early Termination/Discontinuation**

If a subject is discontinued from the study prior to Visit 3, then all safety evaluations that are to be performed at Visit 3 should be performed on the day of discontinuation (early termination) or at the discretion of the investigator.

Adverse Events (both elicited and observed) and serious adverse events (SAEs) will be monitored throughout the trial. The investigator will promptly review all adverse events (both elicited and observed) for accuracy and completeness. All adverse events will be documented on the appropriate source document and case report form.

If a female reports a pregnancy or has a positive pregnancy test during the study the investigator will notify Ora immediately. The investigator shall request from the subject and/or the subject's physician copies of all related medical reports during the pregnancy and shall document the outcome of the pregnancy. The investigator will retain these reports together with the subject's source documents and will provide a copy of all documentation to Ora. The pregnant subjects will be discontinued from the trial as per the exclusion criteria.

#### 8.4 Schedule of Visits, Measurements and Dosing

8.4.1 Scheduled Visits

Refer to Appendix 1 for a schedule of visits and measurements.

#### 8.4.2 Unscheduled Visits

These visits may be performed in order to ensure subject safety. All procedures performed at an unscheduled visit will be recorded in the source documents and on the Unscheduled Visit eCRF pages. Any procedure indicated in the eCRF that is not performed should be indicated as "Not done."

Evaluations that may be conducted at an Unscheduled Visit include:

- Slit-lamp Biomicroscopy;
- Visual Acuity;
- Intraocular Pressure;
- Urine Pregnancy Test;
- Dilated Fundoscopy;

- Assessment of Adverse Events;
- Assessment of concurrent medications and/or treatments; and
- Any other assessments needed in the judgment of the investigator.

#### 8.5 Subject Disposition

#### 8.5.1 Completed Subjects

A completed subject is one who has not been discontinued from the study and has completed all applicable assessments.

#### 8.5.2 Discontinued Subjects

Subjects may be discontinued prior to their completion of the study due to:

- adverse events
- protocol violations
- administrative reasons (e.g., inability to continue)
- subject choice
- Sponsor termination of study
- other

Note: In addition, any subject may be discontinued for any sound medical reason.

Notification of a subject discontinuation and the reason for discontinuation will be made to Ora and will be clearly documented on the source document.

Discontinuations due to COVID-19 will be indicated as COVID-19 related.

#### 8.6 Study Termination

The clinical trial may be stopped at any time by the investigator, or Ora with appropriate notification.

#### 8.7 Study Duration

An individual subject's participation is estimated to be approximately 2 - 4 weeks.

#### 8.8 Monitoring and Quality Assurance

During the course of the study a monitor, or designee, will make routine site visits to review protocol compliance, assess study drug accountability and storage conditions, subject safety, and ensure the study is being conducted according to the pertinent regulatory requirements. The review of the subjects' medical records will be performed in a manner that adequately maintains subject confidentiality. Further details of the study monitoring will be outlined in a monitoring plan.

Regulatory authorities of domestic and foreign agencies, Ora quality assurance and or its designees may carry out on-site inspections and audits which may include source data checks. Therefore, direct access to the original source data will be required for inspections and audits. All inspections and audits will be carried out giving consideration to data protection as well as subject confidentiality to the extent that local, state, and federal laws apply.

[figure not shown]
# **9 ADVERSE EVENTS**

#### 9.1 Adverse Event

For the purposes of this trial, an adverse event is defined as any untoward medical event occurring after the subject's signing of the informed consent until they are exited from the trial. An adverse event can therefore be any unfavorable and unintended sign, symptom, or disease occurring after the subject started the clinical trial, without any judgment about causality. Any pre-existing medical condition that worsens during the trial will also be considered a new adverse event. Documentation regarding the adverse event should be made as to the nature, date of onset, end date, severity, relationship to study procedure, expectedness, action(s) taken, seriousness, and outcome of any sign or symptom observed by the investigator or reported by the patient upon indirect questioning.

#### 9.1.1 Severity

Severity of an adverse event is defined as a qualitative assessment of the degree of intensity of an adverse event as determined by the investigator or reported to him/her by the patient/subject. The assessment of severity is made irrespective of relationship to study procedures or seriousness of the event and should be evaluated according to the following scale:

#### 9.1.2 Relationship to Study Procedures

The relationship of each AE to the study procedures should be determined by the investigator using these explanations. Decisive factors for the assessment of causal relationship of an AE to the study procedures include, but may not be limited to, temporal relationship between the AE and the procedure, known side effects of the procedure medical history, and/or concomitant medication:

- *Definite:* When there are good reason and sufficient documentation to demonstrate a direct causal relationship between study procedure and AE;
- *Probable:* When there are good reasons and sufficient documentation to assume a causal relationship in the sense of plausible, conceivable, likely but not necessarily highly probable.
- *Possible:* When there is sufficient information to accept the possibility of a causal relationship in the sense of not impossible and not unlikely, although the connection is uncertain or doubtful, for example; due to missing data or insufficient evidence.
- *None:* When there is sufficient information to accept a lack of a causal relationship, in the sense of impossible and improbable.
- *Unclassified:* When the causal relationship is not assessable for whatever reason due to insufficient evidence, conflicting data or poor documentation.

#### 9.1.3 Expectedness

The expectedness of an adverse event should be determined based upon existing safety information about the study procedures. Therefore, the following definition will be used:

- *Unexpected*: An adverse event that is not listed in the safety information available for the study procedure at the specificity or severity that has been observed.
- *Expected*: An adverse event that is listed in the safety information available for the study procedure at the specificity and severity that has been observed.
- *Not Applicable*: Any adverse event that is unrelated to the study procedure.

